10.0 Efficacy Analysis

10.1 General Considerations

The treatment effect will be evaluated based on a two-sided significance level of 0.05 (when rounded to three decimal places).

Efficacy variables will be summarized in all ITT populations. The efficacy analysis will be conducted in the ITT_A and the ITT_B_RR populations. Only the primary and ranked secondary variables will be analyzed for the per-protocol populations using primary approach to handle missing data as described below.

Subjects' actual weight category and prior TNF antagonist exposure will be used as the strata in the stratified analyses.

10.1.1 Analyses of Categorical Variables

For categorical variables, frequencies and percentages will be summarized. The treatment groups will be compared using a Cochran-Mantel-Haenszel (CMH) test with stratification factors as strata for the analysis. The CMH test will use weights proposed by Greenland & Robins, which is calculated as follows:

$$\hat{\delta}_{MH} = \frac{\sum_{i=1}^u w_i \cdot \hat{\delta}_i}{\sum_{i=1}^u w_i}, \text{ where}$$

$$\hat{\delta}_i = \frac{x_i}{n_i} - \frac{y_i}{m_i} \text{ denotes the risk difference in stratum } i, i = 1, \dots, u$$

$$w_i = \frac{n_i \cdot m_i}{n_i + m_i} \text{ denotes the weight of stratum } i, i = 1, \dots, u$$

x_i denotes the number of patients with event in treatment₁ in stratum $i, i = 1, \dots, u$

y_i denotes the number of patients with event in treatment₂ in stratum $i, i = 1, \dots, u$

n_i denotes the number of patients on treatment₁ in stratum $i, i = 1, \dots, u$

m_i denotes the number of patients on treatment₂ in stratum $i, i = 1, \dots, u$

The estimated variance of $\hat{\delta}_{MH}$ is calculated as:

$$\widehat{var}(\hat{\delta}_{MH}) = \frac{\sum_{i=1}^u L_i}{(\sum_{i=1}^u w_i)^2}$$

where $L_i = \frac{x_i(n_i - x_i) m_i^3 + y_i(m_i - y_i) n_i^3}{n_i \cdot m_i \cdot (n_i + m_i)^2}$, $i = 1, \dots, u$

Assuming a normal distribution of $\hat{\delta}_{MH}$, an approximate 95% CI is given as follows, where $z_{0.975}$ is the 97.5% quantile of the standard normal distribution:

$$CI = \left[\hat{\delta}_{MH} \pm z_{0.975} \cdot \sqrt{\widehat{var}(\hat{\delta}_{MH})} \right]$$

Also, the approximate p-value can be calculated using the following:

$$pvalue = 2 \cdot \Pr \left[Z > \left| \frac{\hat{\delta}_{MH}}{\sqrt{\widehat{var}(\hat{\delta}_{MH})}} \right| \right], \text{ where } Z \sim N(0, 1)$$

If there is a stratum for a treatment group that has 0 subjects in any cell in the contingency table, all cells from the stratum will be added by 0.1 in order to prevent dividing by 0 in the above equations, as suggested in Greenland & Robins.

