7.3.1 Primary endpoint analyses

The achievement of PASI 90 at Week 16 is the first co-primary endpoint and is a binary variable with values of 0 or 1. The difference in proportion responding between the BI 655066 arm and the adalimumab arm will be estimated and tested using the Cochran-Mantel-Haenszel risk difference estimate stratified by the randomisation factors of weight (≤ 100 kg

vs. >100 kg) and prior exposure to TNF antagonists (0 vs. ≥1) with weights proposed by Greenland & Robins, which is calculated as follows:

$$\hat{\delta}_{MH} = \frac{\sum_{i=1}^u w_i \cdot \hat{\delta}_i}{\sum_{i=1}^u w_i}, \text{ where}$$

$$\hat{\delta}_i = \frac{x_i}{n_i} - \frac{y_i}{m_i} \text{ denotes the risk difference in stratum } i, i = 1, \dots, u$$

$$w_i = \frac{n_i \cdot m_i}{n_i + m_i} \text{ denotes the weight of stratum } i, i = 1, \dots, u$$

x_i denotes the number of patients with event in treatment₁ in stratum $i, i = 1, \dots, u$

y_i denotes the number of patients with event in treatment₂ in stratum $i, i = 1, \dots, u$

n_i denotes the number of patients on treatment₁ in stratum $i, i = 1, \dots, u$

m_i denotes the number of patients on treatment₂ in stratum $i, i = 1, \dots, u$

The estimated variance of $\hat{\delta}_{MH}$ is calculated as:

$$\widehat{var}(\hat{\delta}_{MH}) = \frac{\sum_{i=1}^u L_i}{(\sum_{i=1}^u w_i)^2}$$

$$\text{where } L_i = \frac{x_i(n_i - x_i) m_i^3 + y_i(m_i - y_i) n_i^3}{n_i \cdot m_i \cdot (n_i + m_i)^2}, i = 1, \dots, u$$

Assuming a normal distribution of $\hat{\delta}_{MH}$, an approximate 95% CI is given as follows, where $z_{0.975}$ is the 97.5% quantile of the standard normal distribution:

$$CI = \left[\hat{\delta}_{MH} \pm z_{0.975} \cdot \sqrt{\widehat{var}(\hat{\delta}_{MH})} \right]$$

Also, the approximate p-value can be calculated using the following:

$$pvalue = 2 \cdot \Pr \left[Z > \left| \frac{\hat{\delta}_{MH}}{\sqrt{\widehat{var}(\hat{\delta}_{MH})}} \right| \right], \text{ where } Z \sim N(0, 1)$$

If there is a stratum for a treatment group that has 0 patients in it, the 0 count will be replaced by 0.1 in order to prevent dividing by 0 in the above equations, as suggested in Greenland & Robins. Comparisons of the BI 655066 arm and adalimumab arm will include both a p-value and 95% confidence interval.

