7.3.2 Secondary endpoint analyses

Key secondary endpoints:

The achievement of PASI 75 at Week 16 is a binary variable with values of 0 or 1. The analysis of this endpoint will be identical to that of the PASI 90 co-primary endpoint detailed in the [Section 7.3.1](#).

The achievement of PASI 100 at Week 16 is a binary variable with values of 0 or 1. The analysis of this endpoint will be identical to that of the PASI 90 co-primary endpoint detailed in the [Section 7.3.1](#).

The achievement of PASI 90 at Week 44 is a binary variable with values of 0 or 1. The analysis of this endpoint will be identical to that of the PASI 90 co-primary endpoint detailed in the [Section 7.3.1](#). Note that this endpoint will only be analysed for patients who are re-randomized at Week 16 (i.e., only for Arm A and Arm B defined in [Section 7.2](#)).

Other secondary endpoints:

Other secondary endpoints will be summarized descriptively.

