4.3 Sample Size

This study is designed to show a benefit of risankizumab over adalimumab in terms of PASI 90 response and static Physician Global Assessment (sPGA) of clear or almost clear (sPGA of 0 or 1) at Week 16. This study is also powered to show a benefit in PASI 90 response at Week 44 between the subjects re-randomized to continue on adalimumab vs. subjects randomized to risankizumab at Week 16.

Based on the assumption that the Week 44 PASI 90 rate will be approximate 40% for adalimumab and 70% for risankizumab for the subjects who are re-randomized at Week 16, a total of 120 subjects will result in > 90% power for the primary efficacy analysis in Part B using a type-I error rate at 5%. See Table 1 sample size calculations for different scenarios. Assuming for those subjects originally randomized to adalimumab the response rate at Week 16 for PASI 90 and PASI 50 are 45% and 85%, respectively, then this leaves approximately 40% of subjects expected to fall in the more than or equal

to PASI 50 and less than PASI 90 range and thus be eligible for re-randomization. This requires that 300 (40% of 300 = 120) subjects be randomized to adalimumab at randomization.

Based on the outcome from Trials 1311.1 and 1311.2, the PASI 90 response rate at Week 16 is assumed to be at least 65% in the risankizumab arm. For the primary analysis comparing risankizumab to adalimumab, sample sizes of 300 per arm will allow for > 90% power assuming 70% and 50% PASI 90 response rates for risankizumab and adalimumab, respectively. See [Table 2](#) for more sample size calculations.

Table 1. Sample Sizes for 90% Power for Testing Against Adalimumab Using PASI 90 at Re-Randomization

Risankizumab	Adalimumab	Delta	Re-Randomization Ratio Risankizumab:Adalimumab = Total N
65%	40%	25%	82:82 = 164
70%	45%	25%	80:80 = 160
70%	40%	30%	56:56 = 112
75%	45%	30%	54:54 = 108
80%	50%	30%	51:51 = 102

Table 2. Sample Sizes for 90% Power for Testing Against Adalimumab Using PASI 90

Risankizumab	Adalimumab	Delta	Randomization Ratio Risankizumab:Adalimumab = Total N
65%	50%	15%	226:226 = 452
70%	55%	15%	217:217 = 434
70%	50%	20%	124:124 = 248
75%	55%	20%	118:118 = 236
70%	45%	25%	80:80 = 160
75%	50%	25%	77:77 = 154

Based on the outcome from Trials 1311.1 and 1311.2, the achievement of sPGA clear or almost clear rate at Week 16 is assumed to be at least 85% in the risankizumab arm.

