10.2 Primary Efficacy Analysis

Primary Efficacy Analysis in Part A:

There are co-primary endpoints to assess the efficacy of risankizumab for the treatment of moderate to severe plaque psoriasis. These are as follows:

- Achievement of $\geq 90\%$ reduction from baseline PASI score (PASI 90) at Week 16
- Achievement of an sPGA of clear or almost clear (0 or 1) at Week 16

The primary null hypotheses are that risankizumab is not different from adalimumab in achieving $\geq 90\%$ reduction from baseline in the Psoriasis Area and Severity Index score (PASI 90) and sPGA of clear (0) or almost clear (1) at Week 16.

The achievement of PASI 90 at Week 16 is the first co-primary endpoint and is a binary variable with values of 0 or 1. The difference in proportion responding between treatment arms will be estimated and tested using the Cochran-Mantel-Haenszel risk difference estimate stratified by the randomization factors of baseline weight (≤ 100 kg versus > 100 kg) and prior exposure to TNF antagonists (0 versus ≥ 1).

The achievement of a sPGA of clear or almost clear at Week 16 is the second co primary endpoint and is a binary variable with values of 0 or 1. The analysis of the sPGA co-primary endpoint will be identical to that of the PASI 90 co-primary endpoint detailed above.

The co-primary endpoints of PASI 90 and sPGA clear or almost clear need to be significant simultaneously. Both endpoints compared to ADA will be tested using a two-sided test with a type I error of 0.05.

The primary analysis will be carried out in the ITT_A Population and the PP_A Population. Non-responder imputation will be used as the primary approach for missing values. LOCF and MI will be performed as sensitivity analyses.

Primary Efficacy Analysis in Part B:

The primary endpoint in Part B is the achievement of PASI 90 at Week 44 for those subjects who are re-randomized at Week 16. This endpoint will be tested independently with a type I error rate of 0.05, for the ITT_B_RR Population. A sensitivity analysis will also be performed on the same endpoint for the PP_B_RR Population.

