10.4 Handling of Multiplicity

The statistical comparisons for the primary efficacy variables and the ranked secondary variables will be carried out in the hierarchical order. This means that statistically significant results (P value ≤ 0.05) for the comparison in the higher rank (primary, then ranked secondary variables) are necessary to initiate the testing of the next comparison in the lower rank. Since a step-down procedure is used, each comparison will be tested at a significance level of 0.05 and overall alpha level of 0.05 will be preserved.

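### In Part B the printed p-value rests on a variance about 7% too small, so the Week 44 PASI 90 test runs at about 5.6–6.3% rather than 5%

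*SAP*

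**What the plan says.** SAP 10.1.1 describes the comparison of categorical endpoints as a stratified CMH test: "The CMH test will use weights proposed by Greenland & Robins, which is calculated as follows". It prints the weighted risk difference, a variance built from the terms x(n−x) and y(m−y), a normal-theory CI, and then the test: "Also, the approximate p-value can be calculated using the following". That p-value is the risk difference over the root of the printed variance, referred to N(0,1). Protocol 7.3.1 prints the same variance and p-value. Protocol 7.3.2 applies them to PASI 90 at Week 44, with the restriction "Note that this endpoint will only be analysed for patients who are re-randomized at Week 16".

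In SAP 10.2 this endpoint is the primary endpoint of Part B (the protocol lists it as a key secondary endpoint): "This endpoint will be tested independently with a type I error rate of 0.05, for the ITT_B_RR Population". SAP 10.4 adds that "each comparison will be tested at a significance level of 0.05 and overall alpha level of 0.05 will be preserved". SAP 4.3 sizes Part B: "a total of 120 subjects will result in > 90% power for the primary efficacy analysis in Part B". SAP 5.2 stratifies the re-randomization by weight and prior TNF antagonist exposure, and SAP 10.1 uses the same two factors in the analysis, which gives four strata.

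**The concern.** A CMH test normally takes its variance from the hypergeometric distribution under the null. The printed test estimates the variance separately in each arm of each stratum and makes no small-sample correction. Each of the eight stratum arms costs one degree of freedom. With 600 patients that is close to negligible; with 120 it is not. A confirmatory test with its own 0.05 allocation would then reject a true null more often than the plan says. A step-down procedure preserves the overall level only if each test in it holds its own level.

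**Working it through.** **Inputs.** From the documents: N=120 in Part B, being 40% of 300; 1:1 re-randomization; two binary factors, so u=4 strata; planned rates of 40% and 70%; two-sided 0.05 (SAP 4.2, 4.3, 5.2, 10.1, 10.2). Assumed, because the documents do not give them: the sizes of the four strata, the block sizes (2, 4, 6), and null rates of 20–30%. Rates of 40–50% are the adalimumab range in SAP Table 1.

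**The plan's own figure.** For 70% vs 40% with a pooled null variance:

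n = [1.960·√(2·0.55·0.45) + 1.282·√(0.21+0.24)]² / 0.30² = (1.379 + 0.860)² / 0.09 ≈ 55.7, so 56 per arm.

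This reproduces the 112 in Table 1. With 60 per arm the same formula gives about 92% power, so the claim of more than 90% holds. An unpooled variance would give (1.960+1.282)²·0.45/0.09 ≈ 52.5, so 53 per arm. The sizing therefore fits a null-variance test better than the test that is printed.

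**Bias of the printed variance.** Let p be the common null rate, q=1−p, and w = nm/(n+m).

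- E[x(n−x)] = n(n−1)pq, so E[L] = pq·(w − c), with c = (n²+m²)/(n+m)².
- The true null contribution of the stratum is pq·w.
- Ratio of expected to true variance = 1 − Σc/Σw. With equal arms c = 1/2 and Σw = N/4, so the ratio is 1 − 2u/N.
- N=120: 1 − 8/120 = 0.933. N=112: 0.929. N=600: 0.987.
- Normal-theory error, 2·[1 − Φ(1.96·√ratio)]: 5.8%, 5.9% and 5.2%.

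With equal arms this does not depend on how patients spread over the strata; unequal arms lower it further. It leaves out the rule that adds 0.1 to a stratum with a zero cell. With that rule the simulated ratio is about 0.93–0.95.

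**Simulation, N=120.** 200,000 trials per setting, five assumed splits (30/30/30/30; 67/17/29/7; 77/13/25/5; 47/31/25/17; 80/24/12/4), with the 0.1 rule in the printed test:

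| Null rate | Printed test | CMH score test | Gain (points) |
|---|---|---|---|
| 20–40% | 5.8–6.2% | 4.8–5.2% | 0.7–1.2 |
| 45% | 5.6–6.1% | 5.0–5.4% | 0.2–0.9 |
| 50% | 5.6–6.1% | 5.0–5.5% | 0.1–0.9 |

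- Arms equal only on average: printed test 6.0–6.3%, CMH 4.9–5.1%.
- Null rates that differ between strata (four assumed patterns, 10–50%): 5.6–6.3% against 5.0–5.1%.
- A separate set of layouts with null rates of 30–70% gave 5.5–6.3% for the printed test.
- Fewer non-empty strata: three give a ratio of 0.950 and 5.6–6.0%; two give 0.967 and 5.3–5.8%.
- Rounding p to three decimals (SAP 10.1) adds at most 0.1 point.
- 95% CI coverage at 20–50%: printed 93.8–94.4%; n−1 variance 94.4–94.8%; Sato 94.3–94.8%.

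**Part A, N=600.** The printed test gives 5.1–5.3% at 40% and 70%. At exactly 50% it gives about 5.5–5.6%, against about 4.9–5.0% for CMH; discreteness accounts for part of that.

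**The case against.** The best case for the plan is that the effect is small and openly approximate. The formula is printed in full, and both p-value and CI are labelled approximate. Power is about 92% for a 30-point difference. At N=120 the two tests reach different decisions in only 0.2–1.1% of simulated trials. The sentence in SAP 10.4 can be read as describing the step-down order rather than small-sample calibration. The present p-value and CI always agree with each other, and the multiple-imputation analysis (SAP 10.1.4) pools a risk difference and its standard error, which a score test does not supply. The protocol prescribes the same formula.

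Much of this stands. The excess is at most about 1.3 points, the gain at 45–50% can be as little as 0.1–0.4 points under some splits, and the change touches more than SAP wording. None of it brings the test to the 0.05 stated for it.

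Three stronger readings are not supported.

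- A reader might infer that the Part A co-primary tests are compromised. At 600 patients the variance shortfall is 1.3% and the error is near nominal at 40% and 70%. The 50% case is a reason for consistency, not a failure.
- A reader might infer that the zero-cell rules are part of the problem. The protocol acts on an empty arm ("If there is a stratum for a treatment group that has 0 patients in it, the 0 count will be replaced by 0.1") and the SAP on any zero cell ("all cells from the stratum will be added by 0.1 in order to prevent dividing by 0 in the above equations"). At null rates of 20–40% the SAP rule moves the error by only about 0.1–0.2 point. At an assumed 5% rate it makes the test conservative, the opposite direction.
- A reader might extend the figures to PASI 100 at Week 44, which uses the same method. The documents give no rate for it, and the error depends on the rate.

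**Conclusion.** The concern holds for Part B. By algebra, before the 0.1 rule, the printed variance is about 7% too small with 120 patients, four strata and near-equal arms. By simulation the Week 44 PASI 90 test then runs at about 5.6–6.3%, with CI coverage of about 94%. The exact figures rest on assumed stratum splits and null rates, and on all four strata being populated; the excess appeared in every setting tried. It would change the conclusion only for a p-value close to 0.05. It should be corrected because a confirmatory test is given its own 0.05 level and the correction is cheap. It does not by itself put the trial's conclusions in doubt.

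**What to change.** Keep the Mantel-Haenszel risk difference, its weights and the four strata. For Part B:

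- Take the p-value from the CMH score statistic on the unadjusted counts. Its numerator, Σ[x − n(x+y)/(n+m)], equals Σw·δ, so only the variance changes, to the hypergeometric one. State in SAP 10.1.1 that this statistic gives the p-value.
- Compute the 95% CI with n−1 and m−1 in the stratum variances (a one-patient arm contributes zero, and a stratum with an empty arm gets no weight), or with the Sato variance. Say that this corrects coverage only partly.
- Use the n−1 variance for the standard error that is pooled in the multiple-imputation analysis.
- Optionally use the same p-value in Part A, for consistency.
- List the change in SAP 14.1 as a departure from protocol 7.3.1 and 7.3.2, before database lock.

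The costs: power at 70% vs 40% and N=120 falls by up to about 1 point, from about 93% to about 92%, and stays above the planned 90%. At N=112 it falls from 91.4–92.1% to 89.6–90.0%, at or just under 90%. The p-value and CI may disagree in at most 0.4% of trials with n−1, or 0.6% with Sato. The rest is SAP text and programming.

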10.1.2 Analyses of Continuous Variables

For continuous variables, the model based mean and standard error will be presented. The Baseline and visit means will also be presented for each treatment group for subjects who have both Baseline and post Baseline visit values. The treatment groups will be compared using ANCOVA with treatment group, Baseline value, and stratification factors in the model.

10.1.3 Analyses of Time-to-Event Variables

Time to first achievement of endpoints will only be performed in ITT_A Populations up to Week 16. The time to event will be calculated as:

- Time to first achievement (with observed event) = [date of first achievement] – [date of the first dose] + 1

- If a subject never attains Endpoint in Part A, that subject's time to first achievement will be censored at the last visit where PASI (or sPGA) was measured

Time to loss-of-response (and time to relapse) endpoints will only be performed in ITT_B_RR Population among those who achieved response at Re-Randomization. The time to failure events will be calculated as:

- Subjects will be a considered as failures if they subsequently lost the response, or discontinue from the study due to AE – "Worsening of disease under study."
- Time to failure events = [date of failure] – [date of the first dose in Part B] + 1.
- Subjects who maintain Endpoint throughout the study, or discontinued from the study due to reasons other than AE – "Worsening of disease under study," will be censored at their last measurement.

Both time to first achieving endpoints and time to loss-of-response endpoints will be analyzed using Kaplan-Meier estimates for each treatment group. In the ITT_A and ITT_B_RR populations, treatments will be compared using stratified Log-rank test.

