4.2 CONCOMITANT THERAPY, RESTRICTIONS, AND RESCUE TREATMENT

4.2.1 Rescue medication, emergency procedures, and additional treatments

There are no special emergency procedures to be followed.

Stable doses of concomitant therapies for chronic conditions, for which neither the condition nor the treatment are judged to exclude the patient from participation (cf. [Section 3.3](#)) are permissible. All concomitant medications should be carefully evaluated by the investigator, and the CML should be contacted when there are questions regarding concomitant medications.

In the event that a patient experiences an intolerable increase of psoriasis, as deemed by the investigator, during the course of the trial the patient will be discontinued from the trial to receive rescue treatment.

In case of adverse events in need of treatment symptomatic therapy according to investigator judgment will be permitted. All concomitant and/or rescue therapies will be recorded on the appropriate pages of the eCRF.

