7.3.3 Further endpoint analyses

Further endpoints will be summarized descriptively, with number and proportion of responders for dichotomous endpoints and mean, median, SD and IQR presented for continuous variables.

Time to onset of *Endpoint*. The time to event will be calculated as:

- Time to first onset (with observed event) = [date of first onset] – [date of first active treatment] + 1
- If a patient never attains *Endpoint* (e.g. PASI 75 or PASI 90), then that patient's time to first onset will be censored at the last visit where the *Endpoint* was measured (e.g. PASI).

Time to Loss of *Endpoint* (from time of randomization), defined using the following algorithm:

- a) Never attains *Endpoint* (Failure at time 0)
- b) After achieving *Endpoint*, patient will be a failure if they subsequently do not achieve *Endpoint* and either discontinue from the study or switch therapy while still not achieving *Endpoint*. Time to failure will be calculated using date of first failure to achieve *Endpoint*.
- c) Patients that take prohibited meds to treat Psoriasis will be counted as failures at the time when they add the prohibited med.
- d) Patients that switch therapy while maintaining response will be censored at their last measurement prior to switching treatment.

- e) Patients who maintain *Endpoint* throughout the study will be censored at their last measurement.

Time to Loss of *Endpoint* (from time of achieving *Endpoint* or from specific point in time) will be defined as above but only for those patients that have achieved *Endpoint*.

All Time to Event endpoints will be presented using Kaplan-Meier curves with comparisons made between treatment groups using stratified Log-Rank test. If needed, further information will be provided in the TSAP.

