- Imputation of missing data. The imputation will be generated for each efficacy endpoint measurement. The variables to be included in the imputation model are: Baseline disease severity (PASI and sPGA), Baseline weight, treatment group, prior TNF exposure, and measurements at each visit from randomization (or re-randomization) up to the end of the analysis period. For each endpoint, 20 'complete' datasets will be generated using SAS PROC MI. The imputed post-baseline measurements will be rounded to the same precision as the observed data before the determination of responder status (e.g., PASI 90).
- Analysis of imputed data sets. A CMH test, stratified by stratification factors, will be used to analyze categorical endpoints in each imputed dataset.
- Synthesis of imputation and analysis results. SAS PROC MIANALYZE will be used to generate the final inferences of the risk difference between treatment groups.

Of note, subjects who discontinued due to AE – "Worsening of disease under study" will be counted as non-responders in all visits thereafter in the NRI and MI analyses, and will have their last observation prior to discontinuation carried forward in the LOCF analyses.

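### Time to first response censors patients who leave for worsening psoriasis at their last assessment; this censoring depends on the outcome and biases the Kaplan-Meier response proportion upward

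*SAP*

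**What the plan says.** Time to first PASI 50, 75, 90, 100 and sPGA 0/1 are further endpoints (Protocol 5.1.3, SAP 10.3.3). They are analysed in ITT_A up to Week 16 by Kaplan-Meier, and "treatments will be compared using stratified Log-rank test" (SAP 10.1.3).

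- **Censoring.** For subjects who do not attain the endpoint in Part A, "time to first achievement will be censored at the last visit where PASI (or sPGA) was measured". Protocol 7.3.3 agrees: "time to first onset will be censored at the last visit where the" endpoint was measured. Neither rule looks at the reason for leaving.
- **Exit for worsening.** If psoriasis increases intolerably, "the patient will be discontinued from the trial to receive rescue treatment" (Protocol 4.2.1).
- **Same leavers, time to loss of response.** "Subjects will be a considered as failures if they subsequently lost the response, or discontinue from the study due to AE", where the adverse event named is worsening of the disease under study (SAP 10.1.3). Only other reasons for leaving are censored.
- **Same leavers, responder analyses.** They "will be counted as non-responders in all visits thereafter in the NRI and MI analyses" (SAP 10.1.4). For LOCF, the same section uses the value seen before they left.

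**The concern.** Kaplan-Meier and the log-rank test assume that a censored subject would have gone on to respond at the same rate as those still under observation. A patient taken out because the psoriasis got worse is the least plausible candidate for that assumption. The SAP recognises this group by name and counts it as failing in the loss-of-response, NRI and MI rules, but gives it no special handling for time to first response. No sensitivity analysis covers the gap.

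At stake are the published response curves, their Week 16 values and the log-rank p-values for these endpoints. The co-primary and ranked endpoints do not use this rule.

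**Working it through.** **Plan figure first.** The documents give no number for the time-to-first-response analysis. The rates used below (PASI 90 at Week 16: 70% vs 50%) are those of SAP 4.3, Table 2, which states 124 per arm for 90% power. With pooled variance under the null, n = [1.960·√(2·0.60·0.40) + 1.282·√(0.70·0.30 + 0.50·0.50)]² / 0.20² = (1.358 + 0.869)² / 0.04 = 124. This reproduces.

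**Inputs.** PASI/sPGA visits in Part A are at Weeks 4, 8, 12 and 16 (SAP Table 4), with 300 per arm. The rate of leaving for worsening is not given; 1% to 10% is assumed. The response patterns before Week 16 are also assumed.

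**Bias in one arm.** Let F be the Week 16 cumulative response among those who stay and F_k their response by visit k. A fraction d leaves after visit k and never responds. The true proportion is (1−d)F. After visit k only stayers are at risk, so

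1−KM = 1 − [1−(1−d)F_k]·(1−F)/(1−F_k)

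and the excess over (1−d)F simplifies to

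bias = d·(F−F_k)/(1−F_k).

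This is the fraction leaving times the chance that a not-yet-responding stayer still responds by Week 16. It is positive whenever responses occur after visit k.

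| Assumed response at Weeks 4/8/12/16 | Factor, exit after Week 4 | after Week 8 | after Week 12 |
|---|---|---|---|
| 5/20/37/50% | 0.45/0.95 = 0.474 | 0.30/0.80 = 0.375 | 0.13/0.63 = 0.206 |
| 10/38/60/70% | 0.60/0.90 = 0.667 | 0.32/0.62 = 0.516 | 0.10/0.40 = 0.250 |
| 20/50/65/75% | 0.55/0.80 = 0.688 | 0.25/0.50 = 0.500 | 0.10/0.35 = 0.286 |

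Multiplying the smallest factor (0.206) and the largest (0.688) by d gives 0.2 to 0.7 points at 1%, 0.4 to 1.4 at 2% and 1.0 to 3.4 at 5%.

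**Effect on the arm difference.** Here the true arm-wide PASI 90 proportions are held at 70% and 50%. The assumed patterns are 10/35/55/70% (risankizumab) and 5/20/37/50% (adalimumab), with leavers split equally over Weeks 4, 8 and 12. Example, adalimumab with 5% leaving (15 of 300, 5 per visit):

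1−KM = 1 − (285/300)(235/280)(179/230)(135/174) = 1 − 0.4814 = 51.86%, an excess of 1.86 points.

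| Leaving, risankizumab / adalimumab | Excess (points) | Estimated difference (true 20.0) |
|---|---|---|
| 1% / 1% | 0.52 / 0.36 | 20.2 |
| 2% / 2% | 1.05 / 0.72 | 20.3 |
| 5% / 5% | 2.75 / 1.86 | 20.9 |
| 1% / 5% | 0.52 / 1.86 | 18.7 |
| 2% / 10% | 1.05 / 3.94 | 17.1 |

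With equal rates the excess is larger in the better arm. The two excesses are equal when the adalimumab rate is about 1.45 times the risankizumab rate; beyond that the difference is understated. With 1% / 5%, moving all exits to Week 4 or all to Week 12 gives 18.2 or 19.2. Keeping the leavers in the risk set to Week 16 returns 70.0% and 50.0%.

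**Which day to censor at.** The Week 16 window is Rx Days 100 to 127 (SAP Table 4). I simulated visits uniform within ±3 days, the 10/38/60/70% pattern, and 5% leaving at Weeks 4, 8 or 12 (true proportion 0.95 × 70% = 66.5%). Final 1−KM was 79.6% under the SAP rule, 78.2% with leavers censored at Day 113 and 72.7% at Day 127. With no leavers it was 80.3% against a true 70%, so much of the excess on the day scale is not due to leavers.

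**The case against.** **The SAP is not uniform, because LOCF carries the last value forward.** True of the text, but it does not help here. The censoring rule applies only to subjects who never reached the endpoint, so any post-baseline value carried forward is itself a non-response. As-observed analysis is specified only for continuous variables.

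**The SAP follows the protocol.** This stands. Protocol 7.3.3 has the same rule, so a change has to be declared as a departure.

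**Small and low in rank.** This stands. At 1% to 2% leaving the excess is 0.2 to 1.4 points, against a standard error of √(0.5·0.5/300) = 2.9 points for a 50% rate. Response at each visit is also analysed with NRI. Protocol 6.2.3.1 asks leavers to complete end-of-treatment procedures, which include PASI/sPGA; this can move their censoring date later and shrink the bias.

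**Visit-day scatter matters more.** This also stands. When time is counted in actual days, subjects not responding at Week 16 are censored on their own visit day, which inflates the end of the curve even with no leavers. The visit-level figures isolate the leaver effect and do not describe the whole day-scale error.

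**Stronger readings to avoid.** A reader might infer that the bias is largest in the worse arm and so understates the treatment difference. The documents give no leaving rate by arm, and with equal rates the opposite holds. A reader might also take disagreement between these curves and the Week 16 NRI rates as proof of error. First achievement is cumulative: a patient who responds at Week 8 and has lost response by Week 16 counts as an event here and as a Week 16 non-responder there. NRI also fails other dropouts. The two would differ under any censoring rule.

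**Conclusion.** The point holds as a minor inconsistency with a known direction within each arm. Leaving for worsening is driven by the outcome, the SAP already treats it as failure or non-response in the loss-of-response, NRI and MI rules, and censoring it here pushes the estimated proportion responding upward. The sizes rest on three assumptions: the leaving rates, the response patterns before Week 16, and that worsening leavers would not have responded by Week 16. The direction within an arm needs only that they would have responded less often than those who stayed. The direction of the effect on the arm difference cannot be stated in advance. No co-primary or ranked conclusion depends on it.

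**What to change.** In SAP 10.1.3, add that subjects who discontinue for the adverse event of worsening of the disease under study without having reached the endpoint are censored at the end of the Week 16 analysis window, Rx Day 127. They then remain in the risk set as non-responders through all Week 16 assessments. Day 113 would not do this, because it drops them before responses first recorded on Days 114 to 127. List the rule in SAP 14.1 as a change from Protocol 7.3.3.

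The cost is one sentence, a small programming change and slightly lower response curves. The change does not remove the separate visit-day effect described above.
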